4.5 Determination of Sample Size

A total of 230 subjects (80 cognitively healthy volunteers, 80 MCI and 70 AD) will be enrolled in the Exploratory Phase of this study. To explore the Flortaucipir SUVR values across age strata among cognitively healthy subjects, these subjects will be divided into 5 age groups as 20-40 years old, 50-59 years old, 60-69 years old, 70-79 years old and 80 years old or above. There will be 15 subjects in each of the 50 or older age groups and about 20 subjects from age group 20-40 years old. From a preliminary analysis of study T807000, the standard deviation (SD) of SUVR from combination region of interest (ROI) was 0.06 for subjects with low probability of AD. Therefore assuming a 0.06 SD, a sample of 15 subjects will give an approximately 90% probability to observe a 95% confidence interval as accurate as +/-0.04 around the point estimation.

From previous studies, the amyloid positive rate is approximately 50% among MCI patients and approximately 80% from AD subjects. Therefore 80 MCIs and 70 ADs will likely result in 40 amyloid positive MCIs and 56 amyloid positive ADs. Also from study T807000, the combination ROI SUVR difference between CN and AD was 0.39, with a pooled SD of 0.27. Assume a pooled SD of 0.30, a sample of 60 CNs and 56 amyloid positive ADs will give a 90% power to detect a 0.18 difference between the CN and AD groups.

5 CHANGES IN THE CONDUCT OF THE STUDY OR PLANNED ANALYSES

5.1 Changes in the Conduct of the Study

There were no changes in the conduct of the study at the time of preparing this statistical analysis plan.

5.2 Changes from the Analyses Planned in the Protocol/CIP

The protocol was amended (version 07 August 2015, Amendment 2). In this amendment the study was divided into two phases, exploratory (first) phase and confirmatory (second) phase. Currently, this SAP provides the planned analyses for the exploratory (first) phase of the study.

6 BASELINE, EFFICACY AND SAFETY EVALUATIONS

6.1 Schedule of Evaluations

Exploratory (First) Phase and Confirmatory (Second) Phase:

Evaluations	Screening Visit ^a	Florbetapir F 18 Imaging Visit ^b	End of Florbetapir F 18 Imaging (prior to discharge)	Follow-up Phone Call	¹⁸ F-AV-1451 Imaging Visit ^b	End of ¹⁸ F-AV-1451 Imaging (prior to discharge)	Follow-up Phone Call
Signed Consent	X						
Demographics	X						
Medical History/Neurologic Disease History	X						
Concomitant Meds	X	X			X		
Physical Exam/ Neurological Exam	X						
ECG	X				X ^c	X	
Vital Signs	X ^d	X ^e			X ^f	X ^g	
Safety Labs	X				X ^h	X	
Serum beta-hCG ⁱ	X						
Urine Pregnancy test ^j		X			X		
OSU TBI-ID	X						
MMSE	X						
ADAS-Cog 11	X						
Neuropsych battery ^k	X						
MRI of the brain	X						
PET Brain Scan		X			X		
ApoE					X		
Genetic sample					X		
Optional CSF	X ^l						
Evaluation by a physician	X	X ^m	X ^m		X	X	
Adverse Events	X	X	X	X	X	X	X
Serious Adverse Events	X	X	X	X	X	X	X

- a. Screening may take place over several days. All assessments must be performed within 30 days of the first ¹⁸F-AV-1451 imaging session (with the exception of the MRI if previously performed).
- b. The ¹⁸F-AV-1451 and florbetapir F 18 imaging sessions must be performed at least 48 hours apart, but the order of the scans is interchangeable.
- c. Two ECGs will be taken approximately 5 minutes apart immediately prior to (within approximately 10 minutes) ¹⁸F-AV-1451 Injection administration. One will be taken within 5 minutes after completion of injection.
- d. Screening vital signs include pulse rate, respiratory rate, supine blood pressure, height and weight
- e. Vital signs (pulse rate, respiratory rate, supine blood pressure, weight) will be taken immediately prior to injection of florbetapir F 18.
- f. Pulse, respiratory rate, supine blood pressure, temperature and weight will be taken immediately prior to administration of ¹⁸F-AV-1451. Pulse, respiratory rate, and supine blood pressure within 5 minutes after completion of injection of ¹⁸F-AV-1451 Injection.
- g. Pulse, respiratory rate, supine blood pressure, temperature
- h. Blood and urine samples will be collected prior to administration of ¹⁸F-AV-1451 Injection.
- i. Serum beta-hCG pregnancy test at screening (for females of childbearing potential defined as pre-menopausal or less than 2 years post-menopausal and not surgically sterile).
- j. For women of childbearing potential, a negative urine pregnancy test must be obtained within 24 hours prior to florbetapir F 18 injection and within 24 hours prior to ¹⁸F-AV-1451 injection.
- k. Including CDR for subjects in the Confirmatory Cohort.
- l. CSF collection may occur after the subject has passed screening procedures for subjects in the Exploratory Cohort only
- m. A physician or physician designee

**Longitudinal Component
 Exploratory (First) Phase Only:**

Evaluations	5 Month Follow-up Phone Call	9 (+/-2) Months First Longitudinal Follow-up Visit	14 Month Follow-up Phone Call	18 (+/-2) Months, Second Longitudinal Follow-up Visit
Updated Medical History	X	X	X	X
Updated Concomitant Meds	X	X	X	X
ECG		X ⁿ		X ⁿ
Vital Signs		X ^o		X ^o
Safety Labs		X ^p		X ^p
Urine Pregnancy test ^q		X		X
MMSE		X		X
ADAS-Cog 11 ^r		X		X
Neuropsych battery, including CDR ^r		X		X
MRI of the brain ^f		X		X
PET Brain Scan		X		X
Follow-up Phone Call ^s		X		X
Evaluation by a physician		X		X
Adverse Events		X		X
Serious Adverse Events		X		X

The First and Second Longitudinal Follow-up Visits will be performed over several days.

- n. Two ECGs will be taken approximately 5 minutes apart immediately prior to (within approximately 10 minutes) ¹⁸F-AV-1451 Injection administration. One will be taken within 5 minutes after completion of injection. One will be obtained at the end of imaging day
- o. Vital signs include pulse rate, respiratory rate, supine blood pressure, temperature and weight
- p. Blood and urine samples will be collected prior to administration of ¹⁸F-AV-1451 Injection and at the end of the imaging day.
- q. For women of childbearing potential, a negative urine pregnancy test must be obtained within 24 hours prior to ¹⁸F-AV-1451 injection.
- r. ADAS-Cog 11, Neuropsych battery, and MRI can be performed +/- 30 days of the ¹⁸F-AV-1451 scan and within 30 days of each other. Assessments should be performed within the specified window of 9 (+/-2) months or 18 (+/-2) months.
- s. Between 2 or 3 business days of the imaging day

6.2 Time Point Algorithms

6.2.1 Relative Day

The date of first dose of study drug (Flortaucipir) will be considered relative day 1, and the day before the first dose of study drug will be relative day -1. Relative days will be calculated as follows only when the full assessment date is known (i.e., partial dates will have missing relative days):

For days on or after the first dose of study drug:

Date of Assessment – Date of First Dose of Study Drug + 1.

For days before the first dose of study drug:

Date of Assessment – Date of First Dose of Study Drug.

6.2.2 Windows

No window algorithm is being used for this study.

6.3 Screening and Baseline Assessments

Screening may take place over several days. All screening assessments should be performed within 30 days of the initial Flortaucipir PET imaging session (with the exception of the MRI if previously performed). Screening assessments will include:

- Informed consent;
- Demographics (age, gender, race, ethnicity, education, alcohol, drug use, and smoking);
- Medical history, physical and neurological exams, concomitant medications;
- Disease history (date/months since symptom onset, date/months since diagnosis, family history of neurologic disease) for cognitively impaired subjects;
- Ohio State University Traumatic Brain Injury Identification Method (OSU TBI-ID);
- Mini-Mental State Exam (MMSE);
- Safety assessments: Vital signs (pulse rate, respiratory rate, supine blood pressure, height and weight), electrocardiogram (ECG), safety labs (hematology, chemistry, and urinalysis);
- Serum beta-hCG test (for females of childbearing potential defined as pre-menopausal or less than 2 years post-menopausal and not surgically sterile);
- MRI imaging including standard clinical sequences and volumetric MRI;
- Optional CSF collection by LP
- A physician will see the patient during the screening visit.

For efficacy analyses, baseline assessments may be performed at the screening visit or +/- 30 days of the initial Flortaucipir Imaging Visit.

Baseline assessments will include:

- Alzheimer's Disease Assessment Scale- Cognitive subscale (ADAS-Cog11);
- Neuropsychological test battery (Digit Symbol Substitution Test (DSST), Digit span forward and backward , Trail Making A and B, Logical Memory Test, Immediate and Delayed Recall Story A , Animal list generation, Boston Naming Test (BNT) (30 item), American National Adult Reading Test (ANART), Clock Drawing Test, Benton Judgment of Line Orientation test);
- Pfeffer Functional Activities Questionnaire (FAQ). For the MCI and AD groups only.

Tau pathology can be associated with Traumatic Brain Injury (TBI), therefore the OSU TBI-ID (Corrigan and Bogner 2007) short version will be used to screen for a history of traumatic brain injury. It is the briefest version that still provides several summary indices on which the original version was validated. To shorten the instrument, TBIs resulting in loss of consciousness (LOC) are emphasized over less severe injuries. Classifying worst injury based on the OSU TBI-ID will all be displayed. The following classifies worst injury:

- 1= Improbable or possible TBI without LOC- if interview all questions numbered 1-5 are all 'no' or if response to question 6, interview data reports never having LOC, with or without being dazed or having memory lapses.
- 2= Mild TBI with LOC- if in response to question 6, interview data reports LOC does not exceed 30 minutes for any injury.
- 3= Moderate TBI- if in response to question 6 , interview data reports LOC for one injury is between 30 minutes and 24 hours.
- 4= Severe TBI- if in response to question 6, interview data reports LOC for any one injury exceeds 24 hours.

Weight will be displayed in kilograms (kg), height will be displayed in centimeters (cm), and temperature will be displayed in Celsius (C). Weights, heights, or temperatures recorded in alternate units will be converted to the units being displayed using standard conversion formulas. Body mass index (BMI) will be calculated as weight (kg) divided by height squared (cm²).

Each subject's age (years) will be calculated based on his/her date of informed consent and will be truncated to a whole number. Because only year of birth is collected, January 1 will be imputed for the month and day of birth. To calculate age, count the number of months between the date of informed consent and the imputed birthdate. Divide the result by 12 and round down to the nearest integer to get the age of the subject. In

addition, age will be categorized into 5 groups: 20-40 years, 50-59 years, 60-69 years, 70-79 years, and 80 years or older.

The number of years of education for a subject will be calculated for individuals who have specified the level of schooling he/she has obtained. The years of education will be calculated as follows: elementary school = 6 years, middle school = 8 years, high school = 12 years, college/university = 16 years, graduate/master's degree = 18 years, PhD/multiple graduate degrees/medical degree = 20 years. Otherwise, if a subject specified the number of years of education, then this number will be used.

For safety analyses (vital signs, lab and ECG), baseline will be defined as the last assessment recorded on or prior to the start of Flortaucipir.

Baseline for ECGs will be calculated as the average of the two ECGs administered on the imaging day prior to Flortaucipir administration. If only one ECG was administered prior to Flortaucipir administration, the baseline will be defined as the singular ECG administered prior to Flortaucipir administration.

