7.1.4. First and Second Longitudinal Follow-up Visits

Exploratory Phase: The first and second follow-up visits will consist of PET scan procedures, an MRI, cognitive assessments and updated medical history and concomitant medications. The first follow-up scan will occur 9 (+/-2) months following the subject's initial ¹⁸F-AV-1451 scan. The second follow up scan will occur 18 (+/-2) months following the initial ¹⁸F-AV-1451 scan. The cognitive assessments and MRIs should be performed +/- 30 days of each corresponding ¹⁸F-AV-1451 PET imaging visit and within

the 9 (+/-2) months window. The cognitive assessments and MRI should take place in the same 30 day window.

Confirmatory Phase Cohort: The first and second follow-up visits will consist of cognitive assessments and updated medical history and concomitant medications. The first follow-up visit will occur 9 (+/-2) months following the subject's initial ¹⁸F-AV-1451 scan. The second follow-up visit will occur 18 (+/-2) months following the initial ¹⁸F-AV-1451 scan.

Cognitive Assessments: Raters administering the below assessments will be blinded to the ¹⁸F-AV-1451 scans for subjects in the Confirmatory Cohort

- Mini Mental State Exam (MMSE);
- Alzheimer's Disease Assessment Scale- Cognitive subscale (ADAS-Cog11);
- Neuropsychological test battery (Digit Symbol Substitution Test (DSST), Digit span forward and backward ,Trail Making A and B, Logical Memory Test, Immediate and Delayed Recall Story A , Animal list generation, Boston Naming Test (BNT) (30 item), American National Adult Reading Test (ANART), Clock Drawing Test, Benton Judgment of Line Orientation test);
- Clinical Dementia Rating (CDR) Scale; For the MCI and AD groups only.
- Pfeffer Functional Activities Questionnaire (FAQ). For the MCI and AD groups only.

Magnetic Resonance Imaging (MRI) (for Exploratory Phase cohort only)

MRI, including both volumetric and standard clinical sequences, will be obtained at the first and second follow-up visits.

¹⁸F-AV-1451 PET Imaging Session (for Exploratory Phase cohort only)

The first follow-up scan will occur 9 (+/-2) months following the subject's initial ¹⁸F-AV-1451 scan. The second follow up scan will occur 18 (+/-2) months following the initial ¹⁸F-AV-1451 scan. Procedures for the longitudinal follow-up scans will be identical to the initial scan:

- A physician must see the subject prior to administration of ¹⁸F-AV-1451 Injection to determine if they are still suitable to undergo the scan;

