8.2. Safety Analysis

Safety laboratory test results and vital signs measurements will be summarized by subject and by evaluation time point. Change from baseline (pre-dose time point) values will be determined and summarized. Subjects whose laboratory values are outside the pre-determined upper and lower limits of normal will be identified and tabulated.

Adverse events including injection site reactions will be summarized in terms of number and percentage of subjects experiencing an AE. The summary will be further broken down by system organ class (SOC) and preferred term using Medical Dictionary for Regulatory Activities (MedDRA) terms. Adverse events will also be presented by severity, relationship to treatment and seriousness. All subjects who experience SAEs or who discontinue due to AEs will be summarized.

Discontinuation

All subjects who discontinued participation prior to completing the study will be listed and their discontinuation reasons will be tabulated.

Laboratory Data

Changes in laboratory data from Baseline will be summarized. Subjects whose laboratory values are outside threshold values will be identified and tabulated.

Vital Signs

Changes in vital signs from baseline will be summarized.

ECG

Mean changes in ECG parameters will be summarized. The average of the two ECG collected prior to administration of ¹⁸F-AV-1451 on imaging day (-10 and -5 min prior to the administration of ¹⁸F-AV-1451), will be used for the baseline estimate. Any subjects showing QTc > 500 or change from baseline of more than 60 msec will be highlighted.

8.3. ¹⁸F-AV-1451 Image Analysis

All ¹⁸F-AV-1451 PET images obtained at baseline and follow-up starting at 80 minutes post injection will be analyzed. ¹⁸F-AV-1451 PET images starting at 110 minutes post injection, for those subjects in which they were acquired, will also be analyzed. The ¹⁸F-AV-1451 PET images will be spatially normalized to standard stereotactic atlas space using MNI brain atlas. The uptake in tau protein rich brain regions will be assessed with regions of interest (ROI, designed in MNI brain atlas) in terms for standard uptake value ratio (SUVr, normalized by cerebellar uptake). The spatially normalized images and the measured SUVr values will be used to accordingly to accomplish the study objectives.

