4.3 Method of Assignment of Subjects to Treatment Groups

Florbetapir F 18:

All subjects will receive a single IV bolus administration target dose of 370 MBq (10 mCi) of florbetapir F 18 injection.

Flortaucipir:

All subjects except for young cognitive normal (YCN) subjects will receive a single IV bolus administration target dose of 370 MBq (10 mCi) of Flortaucipir injection at each of the baseline, 9 months, and 18 months visits. YCN subjects will only receive a single IV bolus administration of Flortaucipir injection with a target dose of 370 MBQ (10 mCi) at baseline visit.

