6.6.3 Clinical Laboratory Evaluations

Clinical laboratory evaluation will be performed at screening, prior to administration of Flortaucipir injection, and after completion of Flortaucipir imaging for each of the scan sessions, including the makeup scan session if the original planned scan session fail.

Tests will include:

- Hematology (5 mL EDTA): hemoglobin, hematocrit, RBC, WBC, MCH, MCHC, neutrophils, bands, lymphocytes, monocytes, eosinophils, basophils, platelets, morphology, MCV, and RBC morphology.
- Chemistry (6 mL blood): total bilirubin, alkaline phosphatase, ALT (SGPT), AST (SGOT), urea nitrogen, creatinine, glucose, uric acid, calcium, phosphorus, total protein, albumin, total cholesterol, triglycerides, sodium, potassium, bicarbonate, chloride, magnesium, globulin, GGT.
- Urinalysis (10 mL, urine): Samples will be used to assess glucose, RBC, WBC, specific gravity, pH, protein, ketones, urobilinogen, blood, nitrite, microscopic, color, bilirubin, casts, epithelial cells, leukocyte, esterase, and bacteria.
- Serum beta hCG, qualitative: performed at screening for females of childbearing potential who are not surgically sterile. A serum pregnancy test may also be obtained prior to injection at the Imaging Visit if required by the local site.
- Urine beta hCG: performed at the imaging visit(s) prior to injection for females of childbearing potential (defined as pre-menopausal, less than 2 years post-menopausal or not surgically sterile).

- ApoE Genotyping (10ml, blood): will be performed at the initial Flortaucipir imaging session for those subjects whose ApoE results are unknown.

Baseline for clinical laboratory evaluations will be calculated as described in section 6.3. Change from baseline for continuous post-baseline assessments will be calculated as the result at the visit minus the baseline value. For applicable laboratory tests, laboratory values will be defined as low, normal, or high relative to the normal reference ranges for each subject's age and sex. Criteria for potentially clinically significant laboratory results are defined in Appendix 1 of the SAP. A result will be considered potentially clinically significant if the result occurs post-baseline and no test results at or prior to baseline for the parameter in question meet the same criteria for potential clinical significance.

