8.7.3 Clinical Laboratory Evaluations

Laboratory test values from the Flortaucipir imaging session at each time point and for change from baseline to end of study will be displayed using summary statistics (n, mean, SD, median, min, max, 25th pct, and 75th pct). This will be calculated within each diagnostic group and on all subjects. Potentially clinically significant laboratory results will be displayed using frequency and percentage of subjects with the result.

All clinical laboratory data will be presented in listings. Within each listing, laboratory values outside the normal ranges will be flagged as either high (H) or low (L). In addition, shift tables will be presented to display the shift in the normal range categories (L, normal (N), H) from baseline to the final evaluation. Baseline is defined in section 6.3.

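### As most naturally read, the SAP gives labs and vital signs one baseline before the first flortaucipir dose, so end-of-study lab changes span 16 to 20 months for most subjects and one session for others, which does not match Protocol 8.2.

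*SAP*

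**What the plan says.** SAP 6.3 covers vital signs, labs and ECG in one sentence: "baseline will be defined as the last assessment recorded on or prior to the start of Flortaucipir". It then gives ECG its own rule, the mean of the two pre-injection tracings on the imaging day. SAP 6.6.3 (labs) and 6.6.4.1 (vital signs) refer back to 6.3.

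SAP 4.3 has every group except YCN receiving flortaucipir "at each of the baseline, 9 months, and 18 months visits", whereas "YCN subjects will only receive a single IV bolus administration of Flortaucipir injection", at baseline. Labs are drawn "prior to administration of Flortaucipir injection, and after completion of Flortaucipir imaging for each of the scan sessions". Vital signs are taken before injection, within 5 minutes after it, and before discharge.

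SAP 8.7.3 summarises lab change from baseline to end of study, by diagnostic group and for all subjects together, and tabulates normal-range shifts "from baseline to the final evaluation". SAP 8.7.4.1 summarises vital-sign change from baseline at each time point. Under 6.6.3 and 6.6.4.1, a PCS flag needs a post-baseline value that meets the limit and no value at or before baseline that does.

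Protocol 8.2 states for labs and vital signs: "Change from baseline (pre-dose time point) values will be determined and summarized".

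**The concern.** With three tracer injections about nine months apart, the natural acute comparison is each post-injection value against the value just before that injection. The adverse-event rules already follow this logic: Protocol 7.7.2 and SAP 6.6.2 use a 48-hour window after each injection.

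A single first-dose baseline does something else at months 9 and 18. The difference then includes any ageing, disease progression or new medication since enrolment. There is no untreated group, so the design cannot separate these from a tracer effect afterwards. Within-subject, same-session change would not be planned at two of the three sessions, and PCS flags could arise from values taken before the tracer was given that day.

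**Working it through.** The plan states no figure on this point, so the check traces the definition and counts what it produces.

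**1. Which baseline does the text imply?** SAP 6.2.1 fixes the time origin once: "The date of first dose of study drug (Flortaucipir) will be considered relative day 1". No section defines a month-9 or month-18 baseline for labs or vital signs. For labs, the terms end of study and final evaluation in 8.7.3 suggest one endpoint per subject. Only ECG has an imaging-day rule. Together these favour a single baseline before the first dose, but this is an inference: 6.3 speaks of the start of flortaucipir, not the first dose.

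**2. Who is affected?** 230 planned (SAP 4.5) minus about 20 YCN gives about 210 subjects, before dropout. For them, two of three sessions are affected.

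**3. What interval does the change cover?** Protocol 7.1.4 says: "The second follow up scan will occur 18 (+/-2) months following the initial" flortaucipir scan. The first follow-up is at 9 ± 2 months. Scanning starts about 80 minutes after injection and lasts 20, so a session runs about 80 + 20 = 100 minutes from injection to end of scan. One month is 365.25/12 × 24 × 60 = 43,830 minutes.

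| Comparison | Interval | Relative to 100 minutes |
|---|---|---|
| Within one session (YCN; first session for all) | about 100 min plus time to sampling | 1 |
| First follow-up against first-dose baseline | 7 to 11 months | 3,068 to 4,821 |
| Second follow-up against first-dose baseline | 16 to 20 months | 7,013 to 8,766 |

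For subjects completing three sessions, the lab change to end of study and the shift table use only the last row. For YCN they use only the first. The all-subjects summary mixes both.

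**4. How many values count as post-baseline before that day's injection?** Flortaucipir sessions only, per subject with three sessions:
- Labs after the first dose: 1 + 2 + 2 = 5 sets, of which 2 precede that day's injection (2/5).
- Vital signs after the first dose: 2 + 3 + 3 = 8 sets, of which 2 precede that day's injection (2/8).

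The time since the previous flortaucipir injection is 7 to 11 months at the first follow-up. At the second it is at least 16 − 11 = 5 months and at most 20 − 7 = 13 months.

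**5. Where does the baseline enter the PCS flags?** In Appendix 1, most lab limits are absolute values or multiples of the upper normal limit, so the baseline matters only through the exclusion rule. Five urinalysis items graded 0 to 3+ use a change. In Appendix 2, blood pressure and pulse need an extreme value and a change together, temperature and weight use change alone, and respiration uses an absolute limit.

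**6. What happens to precision?** This is an illustration on assumed values, since the documents give no variances. Let reading error have SD 1 and let between-visit variation add SD b. The SD of a same-session change is √2, and that of a change across visits is √(2 + 2b²). The ratio is √(1 + b²), or 1.12, 1.41 and 1.80 for b = 0.5, 1 and 1.5.

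**7. Can weight be assessed within a session?** The flow-chart notes (Protocol 11.2, notes f and g) list weight before the baseline flortaucipir injection but not at the end of imaging. Protocol 7.1.4 makes follow-up scan procedures identical to the initial scan. The 7% criterion can therefore serve only as a between-visit check.

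**The case against.** The strongest reply is that the wording is ambiguous rather than wrong. The SAP writes first dose where it means it (6.2.1 and 8.7.2) but not in the baseline sentence. The final-evaluation wording is confined to labs; 8.7.4.1 has no equivalent for vital signs. Protocol 7.2 (Physician Visit) uses study end for discharge from an imaging session, so even that term is not decisive. SAP 5.2 declares no departure from the protocol's safety baseline. This stands in part: a reader might infer that the SAP rules out a per-session baseline, and the documents do not go that far, least of all for vital signs.

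The harm is also limited. Observed lab values and vital signs are summarised at each time point and listed, so pre- and post-injection group values can be seen at every session. The first session is clean for everyone. Adverse events keep their per-injection window. Change over repeated dosing is a legitimate descriptive summary, and safety is an exploratory objective (SAP 3.1 and 3.2). All of this stands. It does not supply within-subject acute change at the follow-up sessions, or PCS flags confined to values after that day's injection.

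A reader might also infer a rate of false weight signals. If the SD of 18-month percentage weight change were 4 to 6%, a normal model would put 8.0 to 24.3% of subjects beyond ±7%. The documents give no such SD, and a 7% limit makes sense only over the long term. Those flags would be the criterion working as a long-term check, so the figure does not measure spurious tracer effects.

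**Conclusion.** The concern holds as an inconsistency of moderate weight. On the natural reading, up to about 210 of 230 subjects have no planned same-session change from baseline for labs and vital signs at two of three sessions. The end-of-study lab change and shift table compare values 16 to 20 months apart for subjects completing three sessions and within one session for YCN. And 2 of 5 lab sets and 2 of 8 vital-sign sets can raise PCS flags although they precede that day's injection. This matches neither the pre-dose baseline of Protocol 8.2 nor the 48-hour adverse-event window.

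The conclusion rests on reading the start of flortaucipir as the first dose, and on planned numbers and visit windows. If the sponsor meant a per-session baseline, the analysis is sound but SAP 6.3 and 8.7.3 do not say so. The documents do not support a claim that a safety signal would be missed or that a given share of subjects would be falsely flagged. No efficacy conclusion depends on this point.

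**What to change.** - In SAP 6.3, define the lab and vital-sign baseline as the last value before the injection at each flortaucipir session. For ECG, say that the two-tracing mean is taken on each imaging day; the present text does not say which of the three days.
- Compute acute change, shift and PCS flags within session for labs, blood pressure, pulse, respiration and temperature. Restate the PCS exclusion rule in 6.6.3 and 6.6.4.1 relative to that session's baseline.
- Report change and shift from the first-session baseline as a separately labelled long-term summary, and keep the 7% weight criterion only there. Moving every PCS flag to a within-session basis would disable that criterion.
- Align SAP 8.7.3 and 8.7.4.1 with this and reconcile them with Protocol 8.2.

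The data are already scheduled for collection. The cost is SAP wording, one change to the derivation, and one extra set of safety tables.
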